CCI															
CCI	X						X			X		X			
CCI	X						X			X		X			

Abbreviations: → = ongoing/continuous event; AE = adverse event; BMI = body mass index; ECG = electrocardiogram; FSH = follicle stimulating hormone; HIV = human immunodeficiency virus; HR = heart rate; MDS-UPDRS = Movement Disorder Society Unified Parkinson's Disease Rating Scale; CCI = [redacted]; THC = tetrahydrocannabinol; UK = United Kingdom; (X) = procedure to be conducted only in the case of a clinic visit

- a. Refer to the Appendix 7 (Japan-specific Appendix) for additional observation visits to be conducted during the Titration Period. The Week 2 and Week 3 visits must be conducted as clinic visits in Japan.
- b. At the discretion of the investigator and per local regulation, the Week 2 and Week 3 visits may be conducted as phone visits, in which case investigational product will be dispensed by the site to secure courier, and subsequently delivered to the subject following the phone visit. Investigational product will not be dispensed if the protocol specified phone visit has not been performed. Details of the courier process will be included in the study site reference guide. The Week 10 visit may be used as the Screening visit for subjects eligible for the Open Label Extension study, B7601017 (subject to availability), and the Week 15 visit may subsequently be used as Visit 1 (Baseline) of the open label extension study.
1. Informed consent may be obtained up to 60 days prior to Day 0 (Randomization). All other screening procedures should take place within D -45 to D -1. The Screening procedures may be split between multiple days/visits for feasibility and/or subject comfort, however individual procedures should not be split between multiple days/visits.
2. Medical history assessed at Day 0 (Randomization) to confirm no change in history post screening visit.

3. Brief physical will be focused on general appearance, the cardiovascular, respiratory, pulmonary, abdominal exams, as well as directed towards any subject reported symptoms. The brief neurological exam includes observation for cerebellar (intention) tremor and for non-cerebellar tremors (eg, resting or positional), finger to nose, heel to shin, Romberg, gait and tandem walking, positional and gaze evoked nystagmus. Full physical and neurological examination may be performed at the investigator's discretion.
4. Assessed while subject is ON.
5. Weight only assessed at Week 10 visit and Week 17 follow-up visit.

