### 3.1.2. Double Blind Period

Eligible subjects will enter the 15 week double blind treatment phase, consisting of:

- Up to 3 week titration of PF-06649751 or placebo administered once daily to the randomized target dose ([Section 5.5.1](#)).
- 2 week stabilization period for dose adjustment after reaching the target dose with possible return to previous dose level after completion of the titration period. For subjects with intolerable adverse events, adjunct L-Dopa dose may subsequently be reduced after consultation with the Medical Monitor (see Section 5.5.1 [Titration of PF-06649751](#)).
- Period A (Primary Efficacy): a 5 week period of PF-06649751 or placebo administered once daily adjunctive to stable doses of L-Dopa ([Section 5.5.2](#)).
- Period B (Maintenance): a 5 week maintenance period of PF-06649751 or placebo administered once daily adjunctive to stable doses of L-Dopa ([Section 5.5.3](#)).

Subjects will return to the clinic at the end of Weeks 1, 2, 3, 4, 5, 10, 15, and 17. Weeks 2 and 3 may be conducted as phone visits, at the discretion of the investigator.

All other visits will be conducted as phone visits; as per Section 6.5 ([Unplanned Visits](#)), the investigator has the discretion to conduct an unplanned clinic visit if warranted for subject safety. For guidance on concomitant medications for Parkinson's disease and other disorders please see Section 5.8, [Concomitant Treatment\(s\)](#).

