- Register subject as Randomized in IWR system in order to obtain randomization number.
- Dispense Investigational Product. Subjects will begin PF-06649751 or placebo dosing the following morning (Day 1).
- Instruct subjects on continued daily dosing of PF-06649751 or placebo in accordance with randomized dose arm up-titration scheme (see [Table 2](#), Section 5.5.1, [Titration of PF-06649751](#)) and instruct subjects on proper dosing documentation.
- Instruct subjects on continued adjunct stable L-Dopa (open-label) administration.

#### 6.2.2. Dosing: Day 1 through Day 105

- Continued once daily dosing of PF-06649751 or placebo in accordance with randomized dose arm up-titration scheme (see [Table 2](#), Section 5.5.1, [Titration of PF-06649751](#)).
- Continued adjunct stable open-label L-Dopa administration (through Period B).

#### 6.2.3. Titration Period: Day 7

- Dosing compliance verification (Investigational product accountability and documentation) while subject is present to confirm reasons for missed/additional doses. **Based on blister card review and/or tablet count, any subject who is noted not to have taken at least 80% or has taken more than 120% of required doses at any scheduled visit during the study will be considered out of compliance and this must be recorded on the CRF and documented as a Medication Error on the CRF and the source documents.**
- Review and assess adverse events (AEs).
- Assessment of concomitant medications.

- Perform the Columbia Suicidality Severity Rating Scale (C-SSRS) “Since last evaluation”.
- Perform standard supine triplicate 12-lead electrocardiogram (ECG).
- Perform standard single supine and standing vitals (HR and blood pressure).
- Perform MDS-UPDRS Part III.
- Dispense OFF time diary, review instructions including requirement to wait until the next phone visit before completion of the diary.
- Dispense Investigational Product. Next immediate dose level of PF-06649751 or placebo will be taken the next morning.
- Instruct subjects on continued daily dosing of PF-06649751 or placebo in accordance with randomized dose arm up-titration scheme (see [Table 2](#), Section 5.5.1, [Titration of PF-06649751](#)).
- Instruct subjects on continued adjunct stable L-Dopa (open-label) administration.

#### 6.2.4. Titration Period: Day 14

In the case of a phone visit:

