- Instruct subjects on continued daily dosing of PF-06649751 or placebo in accordance with randomized dose arm up-titration scheme (see [Table 2](#), Section 5.5.1, [Titration of PF-06649751](#)).
- Instruct subjects on continued adjunct stable L-Dopa (open-label) administration.
- Review OFF time diary instructions including requirement to complete diary for 3 consecutive days during the following week.

### 6.2.5. Titration Period: Day 21

In the case of a phone visit:

- Dosing compliance verification via phone to confirm reasons for missed/additional doses. **Based on blister card review and/or tablet count, any subject who is noted not to have taken at least 80% or has taken more than 120% of required doses at any scheduled visit during the study will be considered out of compliance and this must be recorded on the CRF and documented as a Medication Error on the CRF and the source documents.**
- Review and assess adverse events (AEs).
- Assessment of concomitant medications.
- Instruct subjects on continued daily dosing of PF-06649751 or placebo in accordance with randomized dose arm up-titration scheme (see [Table 2](#), Section 5.5.1, [Titration of PF-06649751](#)).
- Instruct subjects on continued adjunct stable L-Dopa (open-label) administration.
- Inform the subject that the verification of blister card will be performed the day following the phone visit by the site staff by text, phone or email depending on the site/subject's preference, and remind subjects to bring all used blister cards to the next clinic visit.
- Confirm the completion of the OFF time diary for 3 consecutive days during the past week and remind the subject to bring the completed diary to the next clinic visit.
- Dispense Investigational Product. Next immediate dose level of PF-06649751 or placebo will be taken the next morning following secure courier delivery.

In the case of a clinic visit:

- Dosing compliance verification (Investigational product accountability and documentation) while subject is present to confirm reasons for missed/additional doses. **Based on blister card review and/or tablet count, any subject who is noted not to have taken at least 80% or has taken more than 120% of required doses at any scheduled visit during the study will be considered out of compliance and this must be recorded on the CRF and documented as a Medication Error on the CRF and the source documents.**
- Collect and review OFF time diary while subject is present.

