- Review and assess adverse events (AEs).
- Assessment of concomitant medications.

- Collect blood and urine for safety lab tests.
- Perform standard supine triplicate 12-lead electrocardiogram (ECG).
- Perform standard single supine and standing vitals (HR and blood pressure).
- Perform the Columbia Suicidality Severity Rating Scale (C-SSRS) “Since last evaluation”.
- Dispense Investigational Product. Next immediate dose level will be taken the next morning.
- Instruct subjects on continued daily dosing of PF-06649751 or placebo in accordance with randomized dose arm up-titration scheme (see [Table 2](#), Section 5.5.1, [Titration of PF-06649751](#)).
- Instruct subjects on continued adjunct stable L-Dopa (open-label) administration.

#### 6.2.6. Dose Adjustment: Day 28

- Dosing compliance verification (Investigational product accountability and documentation) while subject is present to confirm reasons for missed/additional doses. **Based on blister card review and/or tablet count, any subject who is noted not to have taken at least 80% or has taken more than 120% of required doses at any scheduled visit during the study will be considered out of compliance and this must be recorded on the CRF and documented as a Medication Error on the CRF and the source documents.**
- Collect and review OFF time diary while subject is present (if first clinic visit since Day 7).
- Review and assess adverse events (AEs).
- Assessment of concomitant medications.
- Perform standard supine triplicate 12-lead electrocardiogram (ECG).
- Perform standard single supine and standing vitals (HR and blood pressure).
- Perform the Columbia Suicidality Severity Rating Scale (C-SSRS) “Since last evaluation”.
- Perform MDS-UPDRS Part III.
- Dispense Investigational Product.

- Instruct subjects on continued daily dosing of PF-06649751 or placebo in accordance with randomized dose arm up-titration scheme (see [Table 2](#), Section 5.5.1, [Titration of PF-06649751](#)).
- Instruct subjects on continued adjunct stable L-Dopa (open-label) administration.
- Dispense OFF time diary, review instructions including requirement to complete diary for 3 consecutive days during the following week.

#### 6.2.7. Dose Adjustment: Day 35

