## Appendix 7. Country-Specific Appendix - Japan

### Schedule of Activities and Study Procedures (Section 6)

For sites in Japan, the Week 2 (Day 14) and Week 3 (Day 21) visits during the Titration Period must be conducted as site (in-clinic) visits. Additionally, two phone visits are required a day after both the Day 0 (Randomization) Visit (Day 1) and Week 1 Visit (Day 7 [+3 day window]) and two additional study site visits are required a day after both Week 2 Visit (Day 14 [+3 day window]) and Week 3 Visit (21 [+3 day window]). Phone visits can optionally be conducted as site visits (eg, for logistical reasons). Subjects should be offered an optional overnight stay at the study site prior to a site visit. Study drug administration on both site visits (day after Week 2 Visit and Week 3 Visit) should occur at the study site. For phone visits, the phone calls should take place approximately 4 hours post-dose. During site visits, the study procedures are to be performed approximately 4 hours post-dose. Afterwards, subjects may be discharged at investigator's discretion if no safety concerns are identified. These visits (Day 1, Day 8, Day 15, and Day 22) are to be conducted in addition to the protocol [Schedule of Activities/Study Procedures \(Section 6\)](#).

Protocol Activity	Japan Specific Visits (including additional observation visits)					
	Rand. Visit	Wk 1 Observation Visit	Wk 2	Wk 2 Observation Visit	Wk 3	Wk 3 Observation Visit
	Day 1 (phone visit or optional site visit)	Day 8 (phone visit or optional site visit)	Day 14 (site visit)	Day 15 (site visit)	Day 21 (site visit)	Day 22 (site visit)
Concomitant medications assessment	X	X	X	X	X	X
AE assessment	X	X	X	X	X	X
Triplicate ECG			X	X	X	X
Supine and standing blood pressure and pulse rate			X	X	X	X
Columbia Suicidality Severity Rating Scale (C-SSRS)			X		X	
Safety Laboratory			X		X	
Dispensing of Investigational Product			X		X	
Investigational Product accountability			X		X	
Investigational Product and L-Dopa dosing documentation			X		X	
PF-06649751 (or placebo) administration	X	→	→	→	→	→
Adjunct L-Dopa (open-label)	→	→	→	→	→	→

### Day 1 and Day 8

- Assessment of concomitant medications.
- Review and assess adverse events (AEs).
- PF-06649751 or placebo administration in accordance with randomized dose arm up-titration scheme (see [Table 2](#), Section 5.5.1, [Titration of PF-06649751](#)).
- Instruct subjects on continued adjunct stable L-Dopa (open-label) administration.

### Day 14

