An average daily OFF time (using 3 days recording the Hauser diary prior to the visit) will be calculated at all time points for each subject, which includes Baseline (prior to Day 0), Week 3, Week 5 and Week 10 (End of Period A), Week 13 (Period B; exists prior to Protocol Amendment 2 only) and also Week 15 (End of Period B). Change from baseline will then be calculated. Week 10 is the primary endpoint.

- Week 3 Hauser home diary data will be collected at the Week 3 visit for subjects randomized prior to Protocol Amendment 2, and at the Week 3 visit for subjects randomized under Protocol Amendment 2, where sites choose to perform an in-clinic visit (instead of a phone visit).
- Week 3 Hauser home diary data will be collected at Week 4 for subjects randomized under Protocol Amendment 2, when sites perform a phone visit for Week 3. The Week 3 phone visit will be used as the nominal visit.

In calculating the average daily OFF time, the following algorithms and rules are applied. (Rescue medication methods below are for all periods through Period A, and additionally Period B for subjects consented under Protocol Amendment 2 prior to entering Period B).

Valid Hauser Diary Days

1. Subjects who do not complete at least 12 awake hours of symptom diary data (not including ASLEEP time) will have that daily data set to missing (i.e. will not be considered as a valid symptom diary day). There will be no imputation of data for these diary days.
2. Any Hauser diary day on which rescue medication was used will NOT be considered a valid symptom diary day. The Hauser diary data reported on that day hereafter referred to as a rescue diary day, will not be used. As described more completely in the instruction for daily OFF time below, baseline data will be used to impute the observed response on these days. (All periods through Period A, and additionally Period B for subjects consented under Protocol Amendment 2 prior to entering Period B).

Entries at 30-minute Intervals (Only for subjects who have ≥ 12 awake hours of Hauser home diary data)

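### Protocol 6.2.6 leaves no step to collect the Week 3 OFF time diary when Day 14 is in clinic and Day 21 is by phone, contrary to the Schedule of Activities and SAP 3.1

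*Protocol*

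**What the plan says.** The Day 28 step in Protocol 6.2.6 is conditional: "Collect and review OFF time diary while subject is present (if first clinic visit since Day 7".

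Visit mode is flexible. Protocol 3.1.2 states: "Weeks 2 and 3 may be conducted as phone visits, at the discretion of the investigator". The Schedule of Activities gives the same option: "At the discretion of the investigator and per local regulation, the Week 2 and Week 3 visits may be conducted as phone visits". Protocol 6.2.4 and 6.2.5 have separate phone and clinic procedures for each visit, and nothing requires the two visits to use the same mode. Japan is the exception. There, under Appendix 7, "the Week 2 (Day 14) and Week 3 (Day 21) visits during the Titration Period must be conducted as site (in-clinic) visits".

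Other places describe what happens to the Week 3 diary:

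- Protocol 6.2.5, Day 21 by phone: the site is to "remind the subject to bring the completed diary to the next clinic visit".
- Schedule of Activities, diary collection row: Day 21 is marked for clinic visits only, and Day 28 is marked without condition. Footnote 20 has the diary completed between Days 14 and 21 and brought to the following clinic visit.
- SAP 3.1: "Week 3 Hauser home diary data will be collected at Week 4 for subjects randomized under Protocol Amendment 2, when sites perform a phone visit". The SAP attaches no condition about how Week 2 was held.

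**The concern.** The Week 3 diary is collected on Day 21 if that visit is in clinic. Otherwise it has to be collected on Day 28. The need for a Day 28 collection therefore depends only on how Day 21 was held. Section 6.2.6 makes it depend on Day 14 as well, because a clinic visit on Day 14 is enough to make its condition false.

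A Week 3 diary could be lost through wording alone. Week 3 is one of three post-baseline diary time points up to the primary endpoint (Weeks 3, 5 and 10). It enters the MMRM whose estimates feed the Bayesian Emax model, and it is a visit in the secondary analysis of daily OFF time. SAP 4.1 also requires at least one post-dose Hauser diary for entry to the Full Analysis Set.

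**Working it through.** The plan states no figure on this point. The check follows the diary through the visits and then runs the four visit-mode combinations against the text.

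**The diary's path**

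1. Day 7 (Protocol 6.2.3): the diary is handed out but not yet filled in. The step reads "Dispense OFF time diary, review instructions including requirement to wait until the next phone visit before completion of the diary". Its reference to a phone visit suggests, as an inference, that Day 14 was pictured as a phone visit.
2. Day 14 (6.2.4), either mode: "Review OFF time diary instructions including requirement to complete diary for 3 consecutive days during the following week". There is no completed diary to collect on Day 14.
3. Day 21 (6.2.5): collected if in clinic. If by phone, completion is confirmed and the subject is reminded to bring the diary.
4. Day 28 (6.2.6): collected only if no clinic visit has taken place since Day 7. A new diary is then dispensed.
5. Day 35 (6.2.7): a general collection step that follows the diary dispensed on Day 28. It does not mention the Week 3 diary.

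**The four combinations**

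| Day 14 | Day 21 | Collected on Day 21? | 6.2.6 condition on Day 28 | Collection point in 6.2.5/6.2.6 | Collection point in Schedule and SAP 3.1 |
|---|---|---|---|---|---|
| Clinic | Clinic | Yes | False | Day 21 | Day 21 |
| Phone | Clinic | Yes | False | Day 21 | Day 21 |
| Phone | Phone | No | True | Day 28 | Day 28 |
| Clinic | Phone | No | False | None | Day 28 |

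The visit text covers 3 of 4 combinations. The Schedule and SAP cover 4 of 4.

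**A second route to the same gap.** If both visits are by phone but an unplanned clinic visit falls between Day 7 and Day 28, the 6.2.6 condition is again false. The minimum procedures for unplanned visits (Protocol 6.5) do not include diary collection.

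**Who can be affected.** Japanese sites cannot, because both visits are in clinic there. Subjects who had these visits before Amendment 2 cannot either, because SAP 2.2 records that Days 14 and 21 were then required clinic visits. The documents do not say how often the remaining sites combine a clinic Day 14 with a phone Day 21, so no count follows.

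**Full Analysis Set.** A subject who leaves before Day 28 has no Day 28 visit, so the clause does not matter for that subject. A subject who reaches Week 5 with a usable diary qualifies through that diary. The exposure is limited to subjects on the clinic/phone path who attend Day 28 and leave before the Week 5 diary.

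**Check of the replacement rule.** If collection on Day 28 is required when Day 21 was by phone, the condition is false, false, true, true down the table. Collection falls on Day 21, Day 21, Day 28 and Day 28, so 4 of 4 combinations are covered. The unplanned-visit route is closed as well.

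**The case against.** The strongest reply is that the diary would probably be collected anyway. The subject has been told on Day 21 to bring it, the Schedule has the site collecting on Day 28, and SAP 3.1 expects it at Week 4. The condition in 6.2.6 does not forbid collection, and the Day 35 step would allow a late pick-up. SAP 3.1 measures the 7-day window from the Week 3 phone visit, so late pick-up alone would not put the diary outside it. This largely stands. A reader might infer from 6.2.6 that these diaries are never collected, or that the whole clinic/phone group loses its Week 3 data. That follows only if sites apply 6.2.6 literally and disregard the other instructions.

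A reader might also take some share of the 198 planned subjects as the number lost. The documents give no share, and 198 is the wrong base because it includes Japanese subjects and those seen before Amendment 2.

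The effect on the primary analysis is limited. Week 10 has its own diary collection. The Week 3 diary falls within titration, when the 15 mg group is taking 7 mg (Protocol Table 2), and the efficacy analyses use observed cases. The early termination visit also includes a diary review, and SAP 5.3 assigns its data to the closest planned visit, which may supply a post-dose diary for some early leavers.

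Finally, one might infer that losses would fall mainly on the top dose, since only that group has a dose step on Day 22. No document states this expectation, and Protocol 5.5.1 provides for a step back to the Week 3 dose level in Weeks 4 to 5, so difficulty after that step need not mean leaving.

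What remains is that one procedural sentence conflicts with three other places in the Protocol and with the SAP.

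**Conclusion.** Wrong as written: a minor internal inconsistency. On a literal reading of 6.2.6, one of four permitted visit-mode combinations has no collection step for the Week 3 diary, while the Schedule, footnote 20, the Day 21 phone instructions and SAP 3.1 all lead to Day 28.

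The possible loss is a single intermediate diary assessment per affected subject, in the MMRM and the secondary OFF time analysis. Full Analysis Set entry is at risk only for the narrow group who attend Day 28 and leave before Week 5. The number affected cannot be computed. The judgement that the Week 10 effect is likely small rests on Week 3 being an intermediate titration visit and on most sites following the Schedule or the Day 21 reminder. The documents do not support a claim of certain data loss or of a threat to the Week 10 result.

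**What to change.** In Protocol 6.2.6, replace the parenthetical condition on the Day 28 diary step with: (if the Day 21 visit was conducted by phone). A condition is still useful, because subjects seen in clinic on Day 21 have already handed the diary in. It only needs to refer to the right visit. The step then agrees with footnote 20 and SAP 3.1, and with the Schedule for every subject whose Week 3 diary is still outstanding.

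The cost is one phrase in the protocol and a short note to sites. No visit or procedure is added, because the subject has already been asked to bring the diary. No change to the SAP is needed.
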